ECG b	X	X	X		X		X		X	X	X
Physical examination j	X									X	X
BMI	X									X	X
Urine pregnancy test b (females of CBP)		X	X		X		X		X	X	X
Serum pregnancy test (females of CBP) b,n	X	X	X		X		X		X	X	X
Serum TSH, T4, T3, FT3, FT4 (Thyroid-related assessments) b,n	X	X	X		X		X		X	X	X
Thyroglobulin and anti-thyroglobulin n,o	X										
PK blood samples k,n		X								X	
Thyroid symptom questionnaire (ThyPRO Questionnaire)	X	X	X		X		X		X	X	
Concomitant medications	X	X	X	X	X	X	X	X	X	X	X

	Screening	Titration Period (Week 0 to Week 18 a )							Stabilization Period (Week 18 a to Week 30 c )			Early Termination
		Visit 1	Visit 2	Visit 3a	Visit 3b d	Visit 4a	Visit 4b d	Visit 5a e	Visit 5b d,e	Visit 6 f	Visit 7 g	
Visit Number	Visit 1	Visit 2	Visit 3a	Visit 3b d	Visit 4a	Visit 4b d	Visit 5a e	Visit 5b d,e	Visit 6 f	Visit 7 g	ET	
Study Week	-3 to 0	0	6	7	12	13	18 d	19	24	30		
Visit Window	---	±3 days	±3 days	±3 days	±3 days	±3 days	±3 days	±3 days	±3 days	±3 days		
Evaluation of thyroid clinical status l	X	X	X		X		X		X	X	X	
Study intervention dispensing		X	X	X	X	X	X	X	X			
Study intervention compliance		X m	X	X	X	X	X	X	X	X	X	
Study intervention collection			X	X	X	X	X	X	X	X	X	X
Potential for dose adjustment				X		X		X				

AE = adverse event; BMI = body mass index; BP = blood pressure; CBP = childbearing potential; ECG = electrocardiogram; ET = early termination; FT3 = free T3; FT4 = free T4; IRB/IEC = institutional review board/independent ethics committee; PK = pharmacokinetic; T3 = liothyronine; T4 = levothyroxine; TSH = thyroid-stimulating hormone

a The Titration Period is at least 18 weeks in duration. Depending on whether a participant requires additional dose titration after Visit 5a, the Titration Period may end at Week 18, 24, 30, or 36 (up to a maximum of 3 additional titrations are allowed starting at Visit 5b).

b These assessments will be pre-dose.

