$$P_h = \left( n_{h1.}^2 \cdot n_{h21} - n_{h2.}^2 \cdot n_{h11} + n_{h1.} \cdot n_{h2.} \cdot (n_{h21} - n_{h11}) / 2 \right) / n_h^2$$

$$Q_h = (n_{h11}(n_{h2.} - n_{h21}) + n_{h21}(n_{h1.} - n_{h11})) / 2n_h$$

The  $100(1 - \alpha)\%$  confidence limits for the stratified proportion difference are

$$\hat{d}_{MH} \pm (z_{\alpha/2} \times \hat{\sigma}(\hat{d}_{MH}))$$

[REDACTED]

[REDACTED]

[REDACTED]

The **Non-Responder Imputation** incorporating multiple imputation to handle missing data due to **Covid-19 (NRI-C)** will be performed for participants who have missing TSH values either at the end of the Titration Period or at the end of the Stabilization Period. The NRI-C will categorize any participant who does not have an evaluation at the end of Titration Period or at the end of Stabilization Period as a non-responder. The only exception is that missing data solely due to COVID-19 infection or logistical restrictions related to the COVID-19 pandemic will be handled by Multiple Imputation (MI) under the Missing at Random (MAR) mechanism.

The analysis using NRI-C will be carried out in the following steps.

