### **Step 1. Imputation**

**Step 1.1 Multiple imputation for TSH values:** 100 imputed datasets of TSH values at the end of Titration Period and the end of Stabilization Period will be generated using SAS PROC MI FCS REG. The random seed 12345 will be used. The following covariates will be included in the imputation model:

- 1) Randomized treatment group
- 2) Stratification group (age  $< 65$  years or  $\geq 65$  years)
- 3) Baseline TSH
- 4) TSH at the end of Titration Period for the imputation of missing TSH at the end of Stabilization Period

**Step 1.2. Imputing Responder Status:** In the imputed datasets from Step 1.1, the responder status (yes/no) will be derived from the TSH values at the end of Titration

Period and the end of Stabilization Period according to the normal reference range (0.45-4.12 mIU/L, inclusive) based on the imputed values with the following exception:

The participants who have missing TSH values either at the end of the Titration Period or at the end of the Stabilization Period for reasons other than solely due to COVID-19 infection or logistical restrictions related to the COVID-19 pandemic, the non-responder status will be assigned to these participants in the imputed datasets regardless of the imputed values.

**Step 2. Analysis:** Each of the 100 imputed datasets from Step 1.2 will be analyzed separately using the above mentioned stratified Mantel-Haenszel test.

**Step 3. Pooling:** The point estimate and 95% confidence interval of the stratified proportion difference from the 100 imputed datasets are combined into one overall result using **PROC MIANALYZE**.

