### **Multiple Imputation**

The Multiple Imputation (MI) analysis will be carried out for all the missing TSH values regardless of reasons for missingness in the steps similar to the ones described above for NRI-C, with the exception of Step 1.2.

**Step 1.2. Imputing Responder Status:** In the imputed datasets from Step 1.1, the responder status (yes/no) will be derived from the TSH values at the end of Titration Period and the end of Stabilization Period according to the normal reference range based on the imputed values.

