## 10.2

## SECONDARY EFFICACY ENDPOINTS

### **The Achievement of Titration TSH Response**

The achievement of titration TSH Response is defined as TSH values that are within the normal reference range of 0.45 to 4.12 mIU/L, inclusive, at the end of the Titration Period (Titration TSH Responder). The secondary estimand is the difference in the percentage of Titration TSH Responders between the Armour Thyroid and synthetic T4 study intervention groups in the ITT population. The number and percentage of titration TSH responders will be summarized by treatment group in the ITT Population along with the 2-sided 95% CI for the stratified proportion difference. The non-inferiority (NI) hypothesis test for the secondary efficacy endpoint, based on the ITT Population, will be performed at a 1-sided 2.5% level of significance (equivalent to a two-sided 5% level of significance). The analysis of the secondary efficacy endpoint will be performed on the ITT Population using stratum-adjusted Mantel-Haenszel by age group (age < 65 years or  $\geq$  65 years) as described in the Section 10.1 (Agresti 2013, p. 231).

The **Non-Responder Imputation** incorporating multiple imputation to handle missing data due to Covid-19 (NRI-C) will be performed for participants who have missing TSH values at the end of the Titration Period similar to the primary efficacy analysis outlined in Section 10.1.

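### The TSH imputation model leaves out on-treatment TSH from Visits 3a, 4a and, above all, 6; adding it is a free improvement that makes missing-at-random easier to defend

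*SAP*

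**What the plan says.** SAP 10.1, Step 1.1: 100 datasets of end-of-Titration and end-of-Stabilization TSH "will be generated using SAS PROC MI FCS REG". Four covariates are listed: "Randomized treatment group", age stratum, baseline TSH, and "TSH at the end of Titration Period for the imputation of missing TSH at the end of Stabilization Period".

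SAP Table 4-1 schedules "Serum TSH, T4, T3, FT3, FT4 (Thyroid-related assessments") at Visits 1, 2, 3a, 4a, 5a, 6, 7 and Early Termination. Footnote e repeats the Visit 5a assessments at 5c, 5e and 5g where titration is extended.

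Use of the imputed values differs by analysis:

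- **Primary (NRI-C):** "missing data solely due to COVID-19 infection or logistical restrictions related to the COVID-19 pandemic will be handled by Multiple Imputation (MI"). For any other missing value, "the non-responder status will be assigned to these participants in the imputed datasets regardless of the imputed values".
- **MI sensitivity analysis:** it "will be carried out for all the missing TSH values regardless of reasons for missingness".
- **NRI-MI sensitivity analysis:** the same imputation, except that discontinuation for lack of efficacy, a drug-related adverse event or death is set to non-response.
- **Secondary endpoint (SAP 10.2):** handled in a way "similar to the primary efficacy analysis outlined in Section 10.1", with MI and NRI-MI counterparts.

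Under SAP 4.1 participants can enter Stabilization once TSH is in range. Protocol 6.6 prohibits dose changes from then on.

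**The concern.** For a missing Visit 7 value, the only on-treatment predictor is the end-of-Titration TSH. For everyone who entered Stabilization by protocol, that was an in-range result. Visit 6 comes six weeks before Visit 7 on the same fixed dose. It is the measurement that could show drift out of range, and the model does not see it.

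Baseline TSH helps little here. It was taken on the participant's own synthetic T4, and inclusion criterion 2.04 requires the Screening value to be in range. For a missing end-of-Titration value the arm term carries the average response on study drug, but no covariate carries the individual's response.

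Missing-at-random is assumed conditional on what is in the model. If missingness is related to Visit 6 TSH, the assumption fails as specified, although the data that would largely repair it are collected. Likely non-responders can then be imputed as responders. If Armour is truly the worse arm, this shrinks the observed deficit, in favour of a non-inferiority claim.

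**Working it through.** The SAP gives no figure for this point, so there is none to reproduce. The documents supply the TSH range (0.45-4.12 mIU/L), the margin (10 points, Protocol 9.4.1.2) and about 142 participants per arm (SAP 4.1). Every SD, correlation, mean and missingness rate below is an assumption.

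**1. Predictors listed and left out**

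| Missing value | Predictors in Step 1.1 | On-treatment TSH left out |
|---|---|---|
| End of Titration | arm, age group, baseline TSH | Visits 3a, 4a |
| End of Stabilization (Visit 7) | the same plus end-of-Titration TSH | Visits 3a, 4a, 6 |

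Under the windows in SAP 16.2, an Early Termination sample that falls in the Visit 6 window is filed as Visit 6, so it goes unused too.

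**2. One participant: end-of-Titration TSH 2.0, Visit 6 TSH 8.0, Visit 7 missing**

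Take log TSH as normal with mean ln 1.6 = 0.470 and SD 0.6. The limits are ln 0.45 = -0.799 and ln 4.12 = 1.416. Set the correlation of end of Titration with Visit 7 at 0.5, of Visit 6 with Visit 7 at 0.7, and of end of Titration with Visit 6 at 0.6.

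- As planned: mean = 0.470 + 0.5 × (ln 2.0 - ln 1.6) = 0.582; SD = 0.6 × √(1 - 0.25) = 0.520. P(in range) = Φ(1.61) - Φ(-2.66) = 0.94.
- With Visit 6: the weights are (0.5 - 0.6 × 0.7)/0.64 = 0.125 on end of Titration and (0.7 - 0.6 × 0.5)/0.64 = 0.625 on Visit 6. Mean = 0.470 + 0.125 × 0.223 + 0.625 × 1.609 = 1.504; SD = 0.6 × √(1 - 0.5) = 0.424. P(in range) = Φ(-0.21) = 0.42.

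Over three correlation sets (0.4-0.6 for end of Titration with Visit 7, 0.7-0.8 for Visit 6 with Visit 7), the planned model gives 0.93-0.95 and the model with Visit 6 gives 0.17-0.42. A second parameter set (mean ln 1.8, SD 0.6-0.7) gives 0.88-0.94 against 0.19-0.51. With a milder Visit 6 value of 5.0, that set gives 0.88-0.94 against 0.54-0.74.

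**3. Effect on the arm difference when all missing Visit 7 values are imputed**

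Simulation on the log scale with 300,000 per arm. Visit 7 is imputed from arm, baseline and end-of-Titration TSH (age group not simulated), then with Visit 6 added. The SDs are 0.6 in both arms (equal) or 0.7 against 0.6, with the larger in the worse arm (unequal). Correlations with Visit 7 are 0.5 for end of Titration and 0.7 for Visit 6. Differences are Armour minus T4, in percentage points.

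| Missingness of Visit 7 | True difference | Bias, planned model | Bias, Visit 6 added |
|---|---|---|---|
| 10%, unrelated to TSH, equal SDs | -3.92 | -0.02 | -0.02 |
| 10%, unrelated to TSH, unequal SDs | -6.95 | +0.39 | +0.22 |
| 5% if Visit 6 in range, 30% if out, equal SDs | -3.81 | +0.32 | -0.01 |
| 5% / 30%, unequal SDs | -7.02 | +0.83 | +0.23 |
| 5% / 60%, unequal SDs | -6.91 | +1.56 | +0.24 |
| 5% / 30%, arms alike | -0.21 (noise) | +0.02 | 0.00 |
| 5% / 30% in T4 arm only, 5% in Armour, unequal SDs | -7.01 | -0.07 | +0.13 |
| 5% / 30%, T4 the worse arm, unequal SDs | +7.07 | -0.82 | -0.18 |

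The part removed by adding Visit 6 is 0.32 - (-0.01) = 0.33, 0.83 - 0.23 = 0.60 and 1.56 - 0.24 = 1.32 points in the three rows where Armour is worse and missingness in both arms depends on Visit 6. The remaining 0.2 or so in the unequal-SD rows comes from the single residual variance shared by the arms, which is a separate matter.

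**4. Scale for the primary analysis**

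NRI-C imputes only values missing solely because of COVID-19. Ignoring the age stratification, one such participant with the profile in step 2 shifts the arm's expected responder rate by (0.94 - 0.42)/142 = 0.37 points, or (0.93 - 0.17)/142 = 0.54 points with the correlation set that favours Visit 6 most. The total depends on how many there are, which the documents do not say.

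**The case against.** The case against rests on five arguments, and most of them stand as limits on size.

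- **A reader might infer that all Visit 5 TSH is ignored.** It is not. The last Visit 5 measurement (5a, 5c, 5e or 5g) is the end-of-Titration value (SAP 4.1 and 16.2) and so is the fourth covariate. If it is out of range, the participant is an observed non-responder and nothing needs imputing. For someone last seen at Week 6 or 12 the SAP does not make clear whether that value becomes the end-of-Titration value; that is a separate question about windows.
- **A reader might infer that dropouts in general are imputed favourably in the primary analysis.** NRI-C makes them non-responders unless the cause is solely COVID-19, and pandemic logistics have no evident link to TSH.
- **A reader might infer that the model always pulls the arms together.** Arm is a covariate. The table shows no pull when the arms are alike, or when TSH-dependent missingness is confined to the T4 arm. When T4 is the worse arm, the shrinkage works against Armour.
- **A reader might infer a larger bias.** Assuming missingness of 4% after an in-range last TSH and 30-40% after an out-of-range one, with true differences of -8.2 and -14.3 points, a simulation can produce 1.5 to 3.1 points. No figure in the documents supports those rates, and they do not describe missingness caused by the pandemic.
- **Missing data are already stress-tested.** All-non-responder, all-responder, complete-case and tipping-point analyses are planned, and none depends on Step 1.1. But none is described as using intermediate TSH either, so none recovers the Visit 6 information.

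What survives is narrow: a relevant, already collected predictor is left out of the model that decides responder status for these participants.

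**Conclusion.** The omission is plain in the SAP and can matter greatly for one kind of participant: in range at the end of Titration, clearly out of range at Visit 6, Visit 7 missing. At a Visit 6 TSH of 8.0, the chance of being imputed a responder is about 90% as planned and roughly 20-50% with Visit 6 in the model.

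The effect on the arm difference is small. It is about zero if the arms are alike or, with similar TSH spread in the arms, if missingness is unrelated to TSH. It is about 0.3-0.8 points toward zero, and about 1.6 in a strong case, if the arms differ and missingness in both depends on the omitted values. Those sizes apply where all missing Visit 7 values are imputed, as in the MI sensitivity analysis and largely in NRI-MI. In the primary analysis the exposure is confined to missingness solely due to COVID-19.

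This is a free improvement, not a flaw that undermines the primary result. The sizes rest wholly on assumed SDs, correlations, arm differences and missingness rates.

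**What to change.** - **SAP 10.1 Step 1.1:** add Visit 6 TSH as an auxiliary predictor of end-of-Stabilization TSH, imputed in the same FCS chain when absent.
- **SAP 10.1 Step 1.1 and the SAP 10.2 counterpart:** add Visit 3a and 4a TSH as auxiliary predictors of end-of-Titration TSH. These are secondary, because an out-of-range value at those visits can lead to a dose change and so relate to a different dose.
- **Do not add 5a, 5c or 5e as separate predictors.** For an 18-week participant 5a is the end-of-Titration value itself, and 5c and 5e exist only for those whose titration was extended.
- Leave the analysis model and the responder rules unchanged.

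The cost is one or two lines in the SAP and extra variables in the PROC MI call, with no new data, visits or participants. It should be fixed before unblinding.

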### ***Sensitivity Analyses for the Primary Efficacy Endpoint***

Participants who are missing TSH values either at the end of the Titration Period or at the end of the Stabilization Period will be assessed by the following sensitivity analyses. Additional sensitivity analyses will be performed if useful and appropriate.

#### **Non-Responder Imputation**

The non-responder imputation sensitivity analysis will be performed to investigate the impact of missing TSH values. If a participant has missing TSH values at either the end of the Titration Period or the end of the Stabilization Period, then this participant will be imputed as a TSH non-responder.

#### **Responder Imputation**

The responder imputation sensitivity analysis will be performed to investigate the impact of missing TSH values. If a participant has missing TSH values at either the end of the Titration Period or the end of the Stabilization Period, then this participant will be imputed as a Sustained TSH responder. If a participant has the TSH value out of the normal reference range at the end of titration or stabilization, the participant will be considered as non-responder by the definition of sustained TSH response regardless of missing data.

#### **Complete Case**

Participants who have not completed the study or who are missing TSH values at either the end of the Titration Period or the end of the Stabilization Period will be excluded from the analysis. That is, the non-inferiority between Armour Thyroid and synthetic T4 will be established in the complete-case.

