6.6. Dose Modification

The clinical practice guidelines for treating hypothyroidism in adults recommend dose adjustments guided by serum TSH levels ([Garber 2012](#), [Jonklaas 2014](#)).

Participants will be randomized to either their pre-randomized dose of synthetic T4 or a corresponding dose of Armour Thyroid (Section [10.10](#), Appendix 10) during the first visit of the Titration Period (Visit 2).

During the Titration Period, Investigators will have the option to up- or down-titrate participants' doses as needed per their interpretation of the participants' TSH levels (normal reference range 0.45-4.12 mIU/L, inclusive). For example, Investigators should up-titrate the dose if the TSH value is above 4.12 mIU/L and down-titrate the dose if the TSH value is below 0.45 mIU/L during the Titration Period.

At Week 18, if participants' TSH levels are not within the normal reference range, the Investigator may up- or down-titrate participants' doses by continuing the Titration Period beyond Week 18. If the Titration Period is continued, the participants' doses can be up- or down-titrated approximately every 6 weeks until their TSH levels are within the normal reference range for up to a maximum of 3 additional titrations (including the titration at Visit 5b). Participants whose TSH levels have not normalized after the maximum 3 additional titrations will not enter the Stabilization Period.

At the end of the Titration Period, participants who are euthyroid based on TSH levels may enter the Stabilization Period.

CONFIDENTIAL

Protocol No. 3014-201-002

Armour Thyroid

Dose modification will be prohibited during the Stabilization Period of the study.

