**Figure 4-1**      **3014-201-002 Study Schematic**

\* If a participant undergoes up to the maximum of 3 additional dose titrations starting at Week 18, the Titration Period may extend up to Week 36; therefore, the Stabilization Period may extend from Week 36 to Week 48 (remaining 12 weeks in duration). The Primary Endpoint will be measured at the end of the Titration Period and the end of the Stabilization Period.

During the Titration Period, study visits are split into parts A and B (i.e., Visit 3a, Visit 3b, Visit 4a, Visit 4b) to allow for any dose titrations:

- Visits 3a and 4a are mandatory for all participants. Study assessments, including bloodwork for total T3, TSH, and study intervention dispensing will be performed.
- Visits 3b and 4b are only required for participants needing a dose titration based on the data obtained from Visits 3a and 4a, respectively. A limited number of assessments and study intervention dispensing will be performed.

Visit 5 is designed as a transition visit between the Titration and Stabilization Periods and may consist of a subset of visits (starting with Visit 5a [Week 18] and extending to Visit 5g [Week 36], as needed). The last visit within Visit 5 serves as both the end of the Titration Period and the beginning of the Stabilization Period.

- Participants with TSH levels within normal reference range at Visit 5a may enter the Stabilization Period (i.e., their next visit will be Visit 6).
- If participants' TSH levels are out of normal reference range at Visit 5a, participants' doses can be up- or down-titrated per the Investigators' interpretation until their TSH levels are within the normal reference range by continuing the Titration Period

beyond Week 18. If the Titration Period is continued, the participants' doses can be up- or down-titrated approximately every 6 weeks until their TSH levels have normalized for up to a maximum of 3 additional titrations (including the titration at Visit 5b). Once their TSH levels are within the normal reference range, participants can enter the Stabilization Period. Participants whose TSH levels have not normalized after the maximum of 3 additional titrations will not enter the Stabilization Period.

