### **10.1**

### **PRIMARY EFFICACY ENDPOINT AND ANALYSES**

The primary efficacy endpoint is the achievement of TSH values within the normal reference range of 0.45 to 4.12 mIU/L, inclusive, at both the end of the Titration Period and the end of the Stabilization Period (sustained TSH responder). The primary estimand is the difference in the percentage of sustained TSH responders between the Armour Thyroid and synthetic T4 study intervention groups in the ITT Population. The number and percentage of sustained TSH responders will be summarized by treatment group in the ITT Population. Participants with a missing TSH value at either the end of the Titration Period or at the end of the Stabilization Period will be handled based on Non-Responder Imputation incorporating multiple imputation to handle missing data due to Covid-19 (NRI-C), as outlined later in this section.

The non-inferiority (NI) hypothesis test for the primary efficacy endpoint, based on the ITT Population, will be performed at a 1-sided 2.5% level of significance (equivalent to a two-sided 5% level of significance). The null hypothesis is that Armour Thyroid is inferior to synthetic T4, which will be tested against the alternative hypothesis that Armour Thyroid is non-inferior to synthetic T4, as follows:

$$H_0: p_A - p_T \leq -\Delta \text{ versus } H_a: p_A - p_T > -\Delta$$

Where:  $p_A$  and  $p_T$  are the proportions of TSH responders in the Armour Thyroid and synthetic T4 study intervention groups, respectively; [REDACTED]

The analysis of the primary efficacy endpoint will be performed on the ITT Population using stratum-adjusted Mantel-Haenszel by age group (age < 65 years or  $\geq$  65 years) as described in ([Agresti 2013, p. 231](#)).

The stratified proportion difference is

$$\hat{d}_{MH} = \left( \sum_h \hat{d}_h w_h \right) / \left( \sum_h w_h \right)$$

where  $\hat{d}_h$  is the proportion difference in stratum h and  $w_h = n_{h1} \cdot n_{h2} / n_h$ .

The proportion difference in stratum h is computed as

$$\hat{d}_h = \hat{p}_{h1} - \hat{p}_{h2} = (n_{h11} / n_{h1.}) - (n_{h21} / n_{h2.})$$

where  $\hat{p}_{h1}$  is the proportion of TSH responder for ATH and  $\hat{p}_{h2}$  is the proportion of TSH responder for synthetic T4 at stratum h.

The variance of  $\hat{d}_{MH}$  as

$$\hat{\sigma}^2(\hat{d}_{MH}) = \left( \hat{d}_{MH} \sum_h P_h + \sum_h Q_h \right) / \left( \sum_h w_h \right)^2$$

where

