### **Stratified Newcombe Confidence Interval**

For the sensitivity analyses of Non-Responder Imputation, Responder Imputation, and Complete Case, the 2-sided 95% confidence interval for stratified proportion difference will also be performed in the ITT Population using stratified Newcombe confidence interval, which is based on a stratified method with Cochran-Mantel-Haenszel weights ([Yan and Su 2012](#)).

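### The complete-case sensitivity analysis drops participants already known to be non-responders because they failed titration

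*SAP*

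**What the plan says.** SAP 10.1 defines a sustained responder as having TSH within 0.45 to 4.12 mIU/L at two time points: the end of titration and the end of stabilization.

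SAP 4.1 (under Figure 4-1) states: "Participants whose TSH levels have not normalized after the maximum of 3 additional titrations will not enter the Stabilization Period". Protocol 6.6 has the same rule. These participants therefore have a TSH at the end of titration but none at the end of stabilization.

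The Complete Case paragraph of SAP 10.1 removes "Participants who have not completed the study or who are missing TSH values at either the end of the Titration Period"; lacking the later value has the same effect. It adds that "the non-inferiority between Armour Thyroid and synthetic T4 will be established in the complete-case". Protocol 9.4.1.2 sets the same exclusion. The stratified Newcombe interval is also computed on this set: "For the sensitivity analyses of Non-Responder Imputation, Responder Imputation, and Complete Case".

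The Responder Imputation paragraph, just before Complete Case, treats the same people differently. If an observed TSH is out of range at either time point, "the participant will be considered as non-responder by the definition of sustained TSH response regardless of missing data". Complete Case has no such sentence.

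**The concern.** A complete-case analysis should show what happens when unknown outcomes are set aside. Here it also sets aside outcomes that are known. Passing titration is a post-randomization result that may depend on treatment, and in a dose-conversion study it is part of what is being tested. As written, the analysis compares sustained response only among those who passed.

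Two things follow within this analysis. An excess of titration failures in one arm disappears from the estimate, whichever arm it is. And the result can differ from the primary result when no outcome is missing, so a reader cannot attribute a difference between the two to missing data. The SAP nevertheless attaches a non-inferiority statement to this set and does not label it as conditional on titration success.

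**Working it through.** **Who is excluded.** Take a participant still out of range after the last permitted titration.

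| Analysis (SAP 10.1) | Treatment of this participant |
|---|---|
| Primary NRI-C, and NRI | Non-responder (no end-of-stabilization TSH) |
| Responder Imputation | Non-responder, stated explicitly |
| MI, NRI-MI | Non-responder: status is derived from both values and the observed one is out of range |
| Complete Case, and Newcombe on it | Excluded |

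The missing end-of-stabilization TSH alone triggers the exclusion, however completion of the study is read.

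**Inputs.** 142 per arm (SAP 4.1); margin 10 points, 1-sided 2.5% (Protocol 9.4.1.2). The readable text gives no titration-failure or retention rates and no complete-case result, so there is no plan figure to reproduce. Assumed: failure proportion f by arm; r = 0.90 of those entering stabilization are in range at its end; no unknown outcomes; no stratification.

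**Formulas.**
- Failures counted: p = (1 - f)r, denominator 142.
- As written: p = r, denominator 142(1 - f).
- 95% limits: d ± 1.96 × √[p₁(1 - p₁)/n₁ + p₂(1 - p₂)/n₂], where d is Armour minus T4.

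**Worked case, f = 8% vs 3%.**
- Counted: 0.92 × 0.90 = 82.8% and 0.97 × 0.90 = 87.3%, so d = -4.5. SE = √(0.828 × 0.172/142 + 0.873 × 0.127/142) = 4.22 points. Lower limit -4.5 - 1.96 × 4.22 = -12.8.
- As written: 90% in both arms on 130.6 and 137.7 participants, so d = 0.0. SE = √(0.09/130.6 + 0.09/137.7) = 3.66 points. Lower limit -7.2.
- Unstratified Newcombe lower limits: -12.9 counted, -7.5 as written.

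| f, Armour vs T4 | Counted: d (95% CI) | As written: d (95% CI) |
|---|---|---|
| 8% vs 3% | -4.5 (-12.8, 3.8) | 0.0 (-7.2, 7.2) |
| 3% vs 8% | +4.5 (-3.8, 12.8) | 0.0 (-7.2, 7.2) |
| 5% vs 2% | -2.7 (-10.6, 5.2) | 0.0 (-7.1, 7.1) |
| 2% vs 1% | -0.9 (-8.3, 6.5) | 0.0 (-7.0, 7.0) |
| 5% vs 5% | 0.0 (-8.2, 8.2) | 0.0 (-7.2, 7.2) |

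**Other retention rates.** At 8% vs 3%, r = 0.85 gives lower limits of -13.5 counted and -8.5 as written; r = 0.95 gives -11.8 and -5.2. At 5% vs 2% with r = 0.95, the counted lower limit is -9.3, inside the margin.

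**The opposite error.** Suppose 7 of 142 fail on Armour and 21 of 142 on T4, with 115 of 135 and 111 of 121 of the remainder responding. As written: 85.2% - 91.7% = -6.6 (Newcombe -14.4, 1.5), so non-inferiority is not met. Counted: 81.0% - 78.2% = +2.8 (-6.6, 12.2), so it is met.

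**Cost of the corrected rule.** Known failures are kept and stabilization dropouts (proportion d', unrelated to outcome) are removed. The estimated rate is (1 - f)(1 - d')r / [f + (1 - f)(1 - d')]. With f = 8% in both arms and dropout of 20% vs 5%, this is 81.2% vs 82.5%, a bias of -1.3 points when the true difference is 0. At f = 5% it is -0.8 and at f = 2% it is -0.3. With 10% vs 5% dropout and f = 8% it is -0.4. The as-written rule gives 0.0 in all four.

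**Early dropouts.** SAP 16.2 defines the last day of titration as the last TSH visit before Visit 6, so an early leaver's last TSH could be taken as an end-of-titration value. Suppose 10% leave early in each arm, f = 5% in both, and the last TSH is out of range in 50% vs 20% of the leavers. Counting these as known failures gives -2.6 (-11.8, 6.5); treating them as undetermined gives 0.0 (-8.6, 8.6).

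**The case against.** **No decision rests on this analysis.** The fixed sequence tests only sustained and then titration response in the ITT Population. The sentence about establishing non-inferiority can be read as merely naming the set. The secondary endpoint measures titration response directly, and on its natural reading its own complete-case rule in SAP 10.2 keeps titration failures, so a difference would be visible elsewhere. All of this stands and limits the point to one analysis. It does not repair that analysis: the SAP 10.2 rule covers a different endpoint.

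**Excluding incomplete records is what complete case means, and the protocol pre-specified it.** True as a description. But the endpoint is composite, and for these participants one value completes it. Responder Imputation already applies that logic.

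**The sizes are assumed.** Correct. Participants enter euthyroid, have several titration opportunities, and Protocol 2.2 reports that in an earlier crossover study all patients stayed in acceptable TSH range. At 2% vs 1% failure nothing crosses the margin, and the 5% vs 2% crossing depends on retention.

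**The remedy is itself biased when stabilization dropout occurs.** Also correct. With 8% vs 3% failure and a true difference of -4.5, it gives -4.9 at equal 10% dropout and -6.0 at 20% vs 5%. These errors are smaller than the 4.5 points lost as written, but they are a reason to report both results.

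**Conclusion.** The concern holds. The complete-case rule and the Newcombe interval on it discard participants whose sustained non-response has been observed, and so condition on successful titration. Given equal retention among those who pass, the whole between-arm difference in titration failure vanishes from the estimate: 4.5 points at an assumed 8% vs 3%, 2.7 at 5% vs 2%, 0.9 at 2% vs 1%. With equal failure only the precision changes. The text establishes the mechanism; the sizes rest on assumed rates, unstratified intervals and no other missing data. The primary conclusion does not change. This should be corrected so that the analysis can be interpreted.

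**What to change.** In SAP 10.1, Complete Case:

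- Exclude only participants whose sustained status is undetermined. Keep as non-responders those with an observed out-of-range TSH at the end of stabilization or at the end of a completed Titration Period, reusing the Responder Imputation sentence.
- State that the last TSH of someone who leaves before the end of titration is not a known failure.
- Run the stratified Newcombe interval on the same set.
- Report titration failures and stabilization dropouts by arm beside the result. SAP 7.0 describes discontinuation for the double-blind period as a whole; the table specifications are in a separate document and may already split it.
- Show the as-written completer result alongside if wanted, labelled as conditional on successful titration.
- Record the departure from Protocol 9.4.1.2 in SAP 17.0.

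The cost is one changed rule, one clarifying sentence, a few counts and one log entry, with no new data. The downside is the small bias under unequal stabilization dropout shown above, which is why both results are useful. The corrected result will be less favourable to Armour Thyroid if that arm has more titration failures, and more favourable if T4 does.
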